8.4.3 UNANTICIPATED PROBLEM REPORTING

Incidents or events that meet the OHRP criteria for UPs require the creation and completion of an UP report form. It is the site investigator's responsibility to report UPs to their IRB and to the DCC/study sponsor. The UP report will include the following information:

- Protocol identifying information: protocol title and number, PI's name, and the IRB project number;
- A detailed description of the event, incident, experience, or outcome;
- An explanation of the basis for determining that the event, incident, experience, or outcome represents an UP;
- A description of any changes to the protocol or other corrective actions that have been taken or are proposed in response to the UP.

To satisfy the requirement for prompt reporting, UPs will be reported using the following timeline:

- UPs that are SAEs will be reported to the IRB and to the DCC/study sponsor within of the investigator becoming aware of the event.
- Any other UP will be reported to the IRB and to the DCC/study sponsor within of the investigator becoming aware of the problem.

• All UPs should be reported to appropriate institutional officials (as required by an institution's written reporting procedures), the supporting agency head (or designee), and OHRP within (insert timeline in accordancy with policy) of the IRB's receipt of the report of the problem from the investigator.

8.4.4 EVENTS OF SPECIAL INTEREST

Not applicable.

8.4.5 REPORTING OF PREGNANCY

Pregnancy is neither an AE nor SAE. All subject pregnancy must be reported to their study doctor or study staff immediately. Once confirmed, study medication will be stopped and the study site will request permission from the woman to follow her for pregnancy outcomes. All confirmed pregnancies will be reported to the study sponsor, FDA, SOBI and IRB and followed until resolution (i.e., termination [voluntary or spontaneous] or birth) to assess for pregnancy-associated AEs or SAEs such as congential anomaly.

8.5 STUDY HALTING RULES

Administration of study agent will be halted when three grade 3 AEs determined to be "probably related" are reported to the FDA/IRB and enrollment screens will stop accepting new study participants. The study sponsor will inform the DSMB members within 24 hours of this occurrence and will provide the DSMB with AE listing reports. The DSMB will convene an ad hoc meeting by teleconference or in writing as soon as possible. The DSMB will provide recommendations for proceeding with the study to the study sponsor. The study sponsor will inform the FDA of the temporary halt and the disposition of the study.

Study Stopping Criteria

- Local intolerance of the administered Kineret or any sign of allergic response.
- Development of signs and symptoms before the second time point preventing the second administration of the study drug.
- Any patient reported drug related SAE after the first or second administration of the study drug.
- Diagnosis with any condition as outlined in the exclusion criteria during the course of the initial 2 weeks of study enrollment.

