	 Local intolerance of the administered Anakinra (Kineret®) or any sign of allergic response. Development of signs and symptoms before the second time point preventing the second administration of the study drug. Any patient reported and drug related SAE after the first or second administration of the study drug. Diagnosis with any condition as outlined in the exclusion criteria during the course of the initial 2 weeks of study enrollment.
Population:	The study population will include up to 40 subjects within 28 days following of injury. The study is open to male and female participants who are between the ages of 14 and 40, who have ACL tears. Participants will be enrolled at the University of Kentucky.

Phase:	2
Number of Sites enrolling	1 (University of Kentucky)
participants:	
Description of Study	IL-1ra (Kineret®, anakinra), supplied by Sobi Pharmaceuticals, is a
Agent :	recombinant, nonglycosylated form of human interleukin-1 receptor antagonist (IL-1Ra). Kineret® consists of 153 amino acids and has a molecular weight of 17.3 kilodaltons. It is produced by recombinant DNA technology using an E coli bacterial expression system. It is available as pre-filled syringes (100 mg in 0.67 mls) and is FDA approved for daily subcutaneous injection (100 mg/day) for treatment of rheumatoid arthritis (age > 10). A total of 1.5 ml (150 mg) will be injected intra-articularly after synovial fluid aspiration 'to dryness' once between 1 and 28 days after ACL injury.
Study Duration:	24-36 months
Participant	2 years
Duration:	•

SCHEMATIC OF STUDY DESIGN

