2.3 POTENTIAL RISKS AND BENEFITS

2.3.1 KNOWN POTENTIAL RISKS

Safety Precautions: Participants will be followed at regular intervals by their study doctor. During each visit participants will be evaluated for adverse events according to GCP guidelines and reported accordingly to IRB and FDA regulations.

Risks associated with Kineret®:

Reproductive Risks: It is not known whether receiving Kineret® is harmful to an unborn child. Pregnancy after administration of Kineret® may involve risks to the mother, and her embryo or fetus. Therefore, females who are capable of reproducing, must use effective contraceptive methods. These methods must be used from the time of screening until Visit 2 during which any remaining medication will be washed out of the joint during the surgery. If the participant does not elect to have surgery (visit 2) contraception methods will be documented until the end of the study. Examples of effective birth control are: hormonal contraceptives (the pill, implant, transdermal patch, or injection), barrier methods (condom with spermicide, diaphragm with spermicide), IUD, or a male partner had a vasectomy.

Lactating women: It is not known whether this drug or its metabolites are excreted in human milk. Because many drugs are excreted in human milk, caution should be exercised when Kineret® is administered to a nursing woman.

Limitations, potential problems, and alternatives: This study will allow for safety and efficacy assessment in patients with acute effusive knee injury.

- Dose: Based on our work and the work of others, we believe 150 mg dosage is appropriate. The goal of the study is to sustain levels of IL-1Ra long enough and a high enough concentrations during the critical, early time period to be effective. For this reason, we have increased our dosage from a single injection (carried out in the preliminary study) to two injections.
- Patient attrition: Close and regular communication, particularly in the intensive first few months, will be provided to all subject participants. Patients will be fully informed of the time commitments and need for a total of three arthrocenteses in order to recruit study subjects willing to participate in the full study. Because arthrocentesis alone can be expected to benefit subjects, education regarding direct and indirect benefits of all aspects of the trial will be provided. Subjects will also receive appropriate compensation for the time and travel.

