7.3 STUDY SCHEDULE

7.3.1 SCREENING/ENROLLMENT

Visit 1 Screening 1-28 days following injury)

- Obtain informed consent and assent, if necessary, of potential subjects
- Review medical history to determine eligibility based on inclusion/exclusion criteria.
- Review medication history to determine eligibility based on inclusion/exclusion criteria.
- Perform medical examinations and collect vital signs as needed to determine eligibility based on inclusion/exclusion criteria. All subjects must have a clinical exam that is consistent with an ACL tear.
- Collection of urine and blood for laboratory testing. Women of child bearing potential will be given a urine pregnancy test. Test must be negative in order to enroll into the study.
- Subjects will have the following assessments: range of motion, knee instability (Lachman's test) and standardized MTP-2 weight bearing x-rays.
- Standard questionnaires including the KOOS, IKDC, VR-12 and a Likert pain scale.
- Research knee MRI

Following the review of above assessment results and a review of inclusion/eclusion criteria, subjects will be randomized into 1 of 3 treatment groups. Following randomizing, subjects will undergo a knee aspiration and will receive their first dose study medication.

Visit 2 (day of surgery or 4-6 weeks post injury)

- Knee aspiration (in the operating room under anesthesia)
- Patient reported outcomes (PROs) administered prior to surgery
- KOOS, IKDC, VR-12 and a Likert pain scale administered prior to surgery
- Biomarkers (urine and blood) pre-operatively
- Review for AE's and SAE's
- ROM will be performed prior to surgery

Visit 3 (4-14 days After Visit 2)

- Knee aspiration (if clinically indicated)
- Biomarkers (urine and blood)
- Review for AE's and SAE's
- ROM will be performed

Visit 4 (6 month After Visit 2+/- 2 weeks)

- Patient reported outcomes (PROs) administered
- KOOS, IKDC, VR-12 and a Likert pain scale administered
- Review for AE's and SAE's

• ROM will be performed

Visit 5 (12 monthsAfter Visit 2+/- 2 weeks)

- ÀRI
- Patient reported outcomes (PROs) administered
- KOOS, IKDC, VR-12 and a Likert pain scale administered
- Biomarkers (serum and urine only)
- Review for AE's and SAE's
- ROM will be performed

Visit 6 (24 month After Visit 2+/- 2 weeks)

- MRI
- Patient reported outcomes (PROs) administered
- KOOS, IKDC, VR-12 and a Likert pain scale administered
- Biomarkers (serum and urine only)
- Review for ÀE's and SAE's
- ROM will be performed

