7.3.2 SCHEDULE OF EVENTS TABLE

This section should capture the procedures that will be accomplished at each study visit and correspond to the descriptions in the above sections.

Procedures	Screening (Visit 1)	Visit 2 ^e	Visit 3	Visit 4	Visit 5	End of Study Visit 6
Time point	1-28 days post injury	Surgery day or 4-6 weeks post injury	4-14 After Visit 2	6 months After Visit 2 (+/- 2 weeks)	12 After Visit 2 (+/- 2 weeks)	24 months After Visit 2 (+/- 4 weeks)
Informed Consent	Х					
Demographics	Х					
Medical history	Х	Х	Х	Х	Х	Х
Randomization	Х					
Administer Investigational Product	Х					
Concurrent meds	Х	Х	Х	Х	Х	Х
Physical Exam	Х					
Range of motion	Х	Х	Х	Х	Х	Х
Vital signs	Х					
Height	Х					
Weight	Х					
Questionnaires	Х	Х		Х	Х	X
Knee Aspiration	Х	Xa	X ^h			
Biomarkers	Х	Х	Х		X ^d	X ^d
Safety Lab Tests ^b	Х					

Procedures	Screening (Visit 1)	Visit 2 ^e	Visit 3	Visit 4	Visit 5	End of Study Visit 6	
Urine pregnancy tests ^c	Х						
Adverse event evaluation	Х	Х	Х	Х	Х	Х	
X-Ray ^f	Х						
MRI ^g	Х				Х	Х	
a: Should a subject be enrolled into the study and choose not to undergo ACL reconstruction aspiration at time of surgery will be omitted. b: Albumin, alkaline phosphatase, total bilirubin, bicarbonate, BUN, calcium, chloride, creatinine, glucose, LDH, phosphorus, potassium, total protein, SGOT [AST], SGPT [ALT], sodium. c: Urine pregnancy test (women of childbearing potential). d: Serum and urine only e. Should a subject be enrolled into the study and choose not to undergo ACL reconstruction, subject will received treatment according to this protocol. For subjects that do not have ACL reconstruction, the time windows will be relative to Visit 2. For example, Visit 3 will be 4-14 days after Visit 2 f. All subjects must have standardized MTP-2 weight bearing x-ray. Documentation of closed growth plates at screening will be noted in the routine SOC x-ray							

g. All subjects enrolled will have an MRI performed regardless if surgery is to be scheduled or not. However, randomization can be performed prior to MRI as the MRI examination is not necessary or required to diagnose the ACL tear.
h. We will only perform the aspiration at Visit 3 if participants had elected to have surgery performed, and if they have fluid on their

knee.

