8.3 TIME PERIOD AND FREQUENCY FOR EVENT ASSESSMENT AND FOLLOW-UP

The occurrence of an AE or SAE may come to the attention of study personnel during study visits and interviews of a study participant presenting for medical care, or upon review by a study monitor. All AEs including local and systemic reactions not meeting the criteria for SAEs will be captured on the appropriate CRF. Information to be collected includes event description, time of onset, clinician's assessment of severity, relationship to study product (assessed only by those with the training and authority to make a diagnosis), and time of resolution/stabilization as well as seriousness of the event. All AEs occurring while on study must be documented appropriately regardless of relationship. All AEs will be followed to adequate resolution.

Any medical condition that is present at the time that the participant is screened will be considered as baseline and not reported as an AE. However, if the study participant's condition deteriorates at any time during the study, it will be recorded as an AE. UPs will be recorded in the data collection system throughout the study.

Changes in the severity of an AE will be documented to allow an assessment of the duration of the event at each level of severity to be performed. AEs characterized as intermittent require documentation of onset and duration of each episode.

The PI will record all reportable events with start dates occurring any time after informed consent is obtained until 7 (for non-serious AEs) or 30 days (for SAEs) after the last day of study participation. At each study visit, the investigator will inquire about the occurrence of AE/SAEs since the last visit. Events will be followed for outcome information until resolution or stabilization.

8.4 **REPORTING PROCEDURES**

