9 CLINICAL MONITORING

Clinical site monitoring will be performed by Bluegrass Research Consultants Inc. The monitor will conduct monitoring to verify that a) the rights and well-being of human subjects are protected; b) the reported trial data are accurate, complete and verifiable from source documents; c) the conduct of the trial is in compliance with the currently approved protocol/amendment(s), Food and Drug Administration (FDA) regulations and ICH guidelines d) Provide practical guidelines for Site Monitors, Study Monitors and Medical Monitors; e) Provide consistent monitoring procedures across all clinical sites; f) Ensure the quality and integrity of clinical study in a timely manner. A monitoring visit report will be provided to the Sponsor within 21 business days following the completion of a visit.

The first monitoring visit will be conducted within two weeks following enrollment of the first subjects. Subsequent monitoring visits will be completed based on enrollment and are expected to occur every four to six weeks.

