10.1.2 ANALYSIS OF THE PRIMARY EFFICACY ENDPOINT(S)

A safety review of treatment Groups 1 and 2will be performed. Safety endpoints will be monitored at each study visit and at each monitoring visit.

Study Stopping Criteria

- local intolerance of the administered Kineret or any sign of allergic response.
- development of signs and symptoms before the second time point preventing the second administration of the study drug.
- Any patient reported SAE after the first or second administration of the study drug.
- Diagnosis with any condition as outlined in the exclusion criteria during the course of the initial 2 weeks of study enrollment.

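### No adverse-event contact is dated between the single injection and Visit 2, and the stopping list is still written for two doses

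*Combined protocol and SAP*

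**What the plan says.** The Protocol Summary has the drug injected "once between 1 and 28 days after ACL injury". Section 2.2 also says once, and the schedule in 7.3.2 marks the investigational product at Visit 1 only. Two places disagree: 2.3.1 speaks of two injections, and 7.3.1 calls the Visit 1 injection a first dose.

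Section 7.3.1 gives the next visit as "Visit 2 (day of surgery or 4-6 weeks post injury"), and the schedule table agrees. Visit 3 is counted from Visit 2. Adverse-event evaluation is marked at Visits 1 to 6 and nowhere between Visits 1 and 2. The MRI that follows Visit 1 (7.1.1) has no adverse-event review attached.

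Enquiry is tied to visits. Section 8.3: "At each study visit, the investigator will inquire about the occurrence of AE/SAEs since the last visit". Section 2.3.1: "During each visit participants will be evaluated for adverse events according to GCP guidelines". Section 10.1.2: "Safety endpoints will be monitored at each study visit and at each monitoring visit". The monitoring visits in the last quote are checks against source documents, and section 9 says: "Subsequent monitoring visits will be completed based on enrollment and are expected to occur every four to six weeks".

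Three undated commitments go further. Section 8.4.1 promises 30 days of toxicity follow-up after treatment ends, 8.6 promises real-time monitoring by investigators and coordinators, and 2.3.1 promises close and regular communication.

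The four-item stopping list appears in the Protocol Summary, 8.5 and 10.1.2. One item is "Diagnosis with any condition as outlined in the exclusion criteria during the course of the initial 2 weeks of study enrollment"; the exclusion conditions in 5.2 include infection and fever. Two other items refer to a second administration.

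**The concern.** The first two weeks after an intra-articular injection are when an injection-related infection or local reaction would be of most concern, and the plan itself singles out two weeks in its stopping list. Yet for many patients nobody is scheduled to ask about such an event inside that period. The participants are as young as 14, and 8.6 rates the risk as greater than minimal. What is at stake is the time to detection and treatment in the affected patient.

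The stopping list has a separate fault. It does not fit a single-dose trial, and its SAE item differs between sections, so staff cannot apply it consistently.

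**Working it through.** The plan states no figure for the interval between Visits 1 and 2, so there is none to reproduce. The check below works from the visit windows.

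**Inputs.** Dosing day *d* = 1 to 28 after injury (Protocol Summary, 7.3.1). Visit 2 = day 28 to 42 on the 4-6 week branch, or surgery day *S* (7.3.1, 7.3.2). Two weeks = 14 days. Enrollment is taken as the injection day, since consent, randomization and injection all belong to Visit 1.

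**4-6 week branch.** The gap runs from 28 − d to 42 − d, so overall from 28 − 28 = 0 to 42 − 1 = 41 days.

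- The shortest gap exceeds 14 when 28 − d > 14, that is d = 1 to 13. Visit 2 is never inside the window.
- The longest gap is at most 14 when 42 − d ≤ 14, that is d = 28 only. Visit 2 is always inside.
- For d = 14 to 27 it depends on the Visit 2 date.

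| Visit 2 on day | Dosing days with gap over 14 | Of 28 dosing days |
|---|---|---|
| 28 | 1-13 | 13 (46%) |
| 35 | 1-20 | 20 (71%) |
| 42 | 1-27 | 27 (96%) |

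These are counts of calendar days, not shares of patients.

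**Surgery-day branch.** The gap is S − d, which is at most 14 only if d ≥ S − 14. Surgery by day 15 covers every possible dosing day. Surgery on day 29 leaves dosing days 1-14 uncovered. Surgery on day 43 or later leaves all 28 uncovered.

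**Earlier trials (section 2.1).** In the group's triamcinolone trial, Table 1 gives mean surgery 28.94 (range 10-51) and mean first visit 4.17 (range 1-8); days are assumed for the table.

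- Mean gap: 28.94 − 4.17 = 24.77, about 25 days. The printed ranges bound it between 10 − 8 = 2 and 51 − 1 = 50.
- That trial's entry was earlier than this protocol requires. The anakinra pilot enrolled at a mean of 15 days (range 6-27), closer to the present window. Set against the same surgery mean, 28.94 − 15 = 13.94, about 14 days. This combines two trials and is an assumption.
- With entry on day 15, the 4-6 week branch gives 28 − 15 = 13 to 42 − 15 = 27 days.

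A fair illustration is therefore a mean gap of about 14 to 25 days for surgical patients, depending on entry timing.

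**Stopping list, side by side.**

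| Item | Protocol Summary | 8.5 | 10.1.2 |
|---|---|---|---|
| Signs that prevent a second administration | present | present | present |
| SAE after first or second administration | must be drug related | must be drug related | no such condition |
| Exclusion diagnosis in first 2 weeks | present | present | present |

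The first row cannot operate when only one dose is given. In the second row, an SAE judged unrelated meets the criterion under 10.1.2 but not under 8.5 or the Protocol Summary.

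**The case against.** The strongest reply is that the plan does provide early follow-up. The 30-day toxicity sentence in 8.4.1 is anchored to treatment and, with one injection, spans the whole two-week window. Sections 8.6 and 2.3.1 add real-time monitoring and close communication, and 8.3 and 8.4.1 allow for events found when patients seek care or report them. An immediate reaction can be recorded at Visit 1 itself. All of this stands as partial cover. None of it names a day, a method or a set of questions, so it does not ensure that any given patient is asked within 14 days.

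A reader might infer that the two-week criterion cannot work. It can: it turns on when the diagnosis was made, and Visit 2 asks about events since Visit 1, so a day-10 diagnosis still meets it in retrospect. For the same reason the documents do not support an inference of lost safety data, and the visit schedule is the same in both arms, so they do not support bias between arms.

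A reader might also infer that each late-found event means a countable number of further patients dosed before a halt. Section 5.5 says only that the stopping criteria may warrant suspension, and the concrete halting rule in 8.5 is three grade 3 events judged probably related. Nothing says that one exclusion diagnosis stops dosing.

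Finally, every participant enters with a painful effusion (5.1), so questions about pain and swelling will produce some non-specific positive answers. That is a real but small cost.

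**Conclusion.** The point holds as one of timing and wording. After the single injection, the next dated adverse-event enquiry can fall up to 41 days later on the 4-6 week branch. It falls beyond 14 days for every patient dosed on days 1-13, and for those dosed on days 14-27 if Visit 2 is late enough. On the surgery branch there is no fixed limit. *Many patients* is the right description. *All patients* would be wrong, because late dosing or early surgery brings Visit 2 inside the window.

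The consequence is possible delay in detecting an early infection or reaction. The documents give no early event rate, so the number of delayed detections cannot be computed.

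The stopping list is wrong as written for a single-dose trial: one inoperable criterion, and one that changes between sections. This reading takes single dosing as intended, on the strength of the Protocol Summary, 2.2 and the schedule table against the two stray phrases in 2.3.1 and 7.3.1. Severity is minor to moderate.

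**What to change.** In one amendment:

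1. Add to 7.3.1 and the schedule table one scripted adverse-event contact by the existing coordinator, by phone or the questionnaire portal described in 7.1.1, within 14 days of injection (for example day 7). Skip it if Visit 2 has already taken place. Ask about fever or infection, worsening knee pain, swelling or redness, allergic reaction, and any new exclusion diagnosis. Pass positive answers to the investigator the same day.
2. In the Protocol Summary, 8.5 and 10.1.2, delete the criterion that depends on a second dose or replace it with a single-dose rule. Make the SAE item refer to the injection, and settle on one wording about drug-relatedness. Correct the two-injection statement in 2.3.1 and the first-dose phrase in 7.3.1.
3. Keep the toxicity sentence in 8.4.1, since it is the only follow-up commitment anchored to treatment. Reword it as 30 days after the injection, tie it to the new contact, and let it stand alongside the recording window in 8.3.

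The cost is one IRB-approved amendment (13.2), one schedule column, edits to a four-item list in three places, three single-sentence corrections, and at most 40 short contacts for the planned enrollment of up to 40. Investigators will also have to review some non-specific positive answers. No new visit, procedure or staff is needed.
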